2.2.2 KNOWN POTENTIAL BENEFITS

There are no expected clinical benefits for the healthy participants who will participate in this trial. There may be benefits to others in the future if the results of this study lead to improved treatment outcomes in preventing people from contracting malaria and in treating patients infected with malaria.

2.2.3 ASSESSMENT OF POTENTIAL RISKS AND BENEFITS

On the basis of the safety provisions and risk minimisation activities outlined in Section 2.2.1, the overall risk to the participants in this trial is considered to be minimal and acceptable, and the potential of future improved treatment for malaria is considered to outweigh these potential risks.

3 OBJECTIVES AND ENDPOINTS

OBJECTIVES	ENDPOINTS
Primary	
To characterise the PK/PD relationship of pyronaridine in healthy participants experimentally infected with blood stage P. falciparum .	The PK/PD relationship between pyronaridine blood concentrations and blood stage asexual parasitaemia.
Secondary	
To evaluate the safety and tolerability of single oral doses of pyronaridine in healthy participants experimentally infected with blood stage P. falciparum .	The safety and tolerability of pyronaridine will be determined by recording the incidence, severity and relationship to pyronaridine of adverse events (as determined by clinical, laboratory and ECG examinations) from Day 8 up to Day 50±2.
To characterise the parasite clearance kinetics following single doses of pyronaridine in healthy participants experimentally infected with blood-stage P. falciparum .	The parasite clearance kinetics following dosing with pyronaridine will be determined by calculating the parasite reduction ratio over a 48 hour period (PRR ₄₈) and corresponding parasite clearance half-life (PCt _{1/2}).
To characterise the pharmacokinetics of pyronaridine following single oral dose administration in healthy participants experimentally infected with blood stage P. falciparum .	The pharmacokinetics of pyronaridine will be determined by calculating the following parameters using non-compartmental methods: C _{max} , T _{max} , t _{lag} , AUC _{0-last} , AUC _{0-∞} , CL/F, Vz/F, λz, t _{1/2} .
To characterise the effect of pyronaridine on P. falciparum 3D7 parasite viability using phenotypic and molecular approaches.	Parasite growth in ex vivo cultures.

4 STUDY DESIGN

4.1 OVERALL DESIGN

This is an open-label, adaptive study that will utilise the *P. falciparum* IBSM model to characterise the PK/PD profile of pyronaridine.

Up to 18 healthy, malaria naïve adult participants are planned to be enrolled into this study, in cohorts of up to six participants each. Following a screening period of up to 28 days, cohorts of up to 6 healthy participants will be enrolled. After confirmation of eligibility, including a Rapid Antigen Test (RAT) for SARS-CoV-2, each participant will be inoculated intravenously on Day 0 with approximately 2,800 viable *P. falciparum*-infected erythrocytes. Participants will be followed up daily via phone call or text message on Days 1 to 3 post-inoculation to solicit any adverse events.

Participants will attend the clinical unit once on Days 4, 5, 6 and 7 for clinical evaluation and blood sampling to monitor the progression of parasitaemia, using quantitative polymerase chain reaction (qPCR) targeting the gene encoding 18S rRNA (referred to hereafter as malaria 18S qPCR). Participants will have a nasopharyngeal aspirate (NPA) for SARS-CoV-2 on Day 6 am. Participants will also have blood collected on Day 7 am to monitor haematology and biochemistry.

Participants will be admitted to the clinical trial unit on Day 8 for dosing with the investigational medicinal product (IMP; pyronaridine) when parasitaemia for the majority of participants is expected to be above 5,000 parasites/mL. Participants will need to return a negative (RAT) for SARS-CoV-2 prior to admission.

Pyronaridine will be administered as a single oral dose. Different doses of pyronaridine will be administered across and within cohorts in order to effectively characterise the PK/PD relationship. Each cohort will comprise up to three dose groups, with participants randomised to a dose group on the day of dosing. The highest dose of pyronaridine administered will be no more than 720 mg; the lowest dose administered will be no less than 180 mg. The proposed dosing regimen for the Cohort 1, assuming six participants are enrolled, is as below. If less than six participants are enrolled the Safety Data Review Team (SDRT) will meet between Day 0 and Day 8, to decide on the dose/s to be administered.

	Dose group		
	1A (n=2)	1B (n=2)	1C (n=2)
Pyronaridine	360 mg	540 mg	720 mg

Each subsequent cohort will be composed of up to 3 dose groups. If more than one dose is tested in a given cohort, subjects will be randomised after inoculation day but prior to Day 8. The dose/s administered to Cohort 2 and Cohort 3 will be selected based on PK/PD and safety data from the preceding cohort/s. The SDRT will review all available safety and tolerability data and PK/PD analysis outcomes from the previous cohort/s, prior to inoculation of the next cohort. The study will conclude when sufficient data have been obtained to define the PK/PD parameters for pyronaridine (the primary endpoint).

A maximum sample size of 18 participants administered pyronaridine is expected to be sufficient to achieve the primary endpoint.

Participants will be confined in the clinical unit for at least 96 h (Days 8 - 12) to monitor the safety and tolerability of pyronaridine dosing and to ensure adequate clinical response against *P. falciparum*. During confinement, regular safety assessments will be performed and blood will be collected to monitor parasite clearance and pyronaridine concentration. If participants are clinically well at the end of the confinement period, they will be discharged and monitored on an outpatient basis up to Day 50±2.

Participants will receive compulsory antimalarial rescue treatment with Riamet® (artemether/lumefantrine) on Day 47±2, or earlier in the following cases:

- Parasitaemia is not reduced by approximately 10-fold at the end of the 96 hour confinement period (Day 12) when compared with peak parasitaemia.
- Parasite regrowth occurs after an initial reduction in parasitaemia, with regrowth defined as ≥ 5000 parasites/mL and a two-fold parasitaemia increase within 48 hours.
- Volunteer discontinuation/withdrawal from the study.
- Investigator's discretion in the interest of participant safety.

Parasite lifecycle stages (including gametocytes) will be monitored at select time points during the study by collecting blood samples and using quantitative reverse-transcriptase polymerase chain reaction (qRT-PCR) targeting parasite lifecycle stage-specific mRNA transcripts.

If gametocytes are present as determined by qRT-PCR any time point after the confinement period, a single dose of Primacin® will be administered at the Investigator's discretion.

If an allergy or contraindication to Riamet® develops, Malarone® (atovaquone/proguanil) will be administered. If in the rare event participants are unable to complete oral antimalarial rescue treatment, they will be admitted to hospital to receive intravenous artesunate.

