
[figure not shown]
	
Team (SDRT) will meet between Day 0 and Day 8, to decide on the dose/s to be administered.
 
  
 	Dose group	
 
 	1A (n=2)	1B (n=2)	1C (n=2)	
   
 Pyronaridine	360 mg	540 mg	720 mg	
  
 
Each subsequent cohort will be composed of up to 3 dose groups. If more than one dose is tested in a given cohort, subjects will be randomised after inoculation day (Day 0) but prior to Day 8. The dose/s administered to Cohort 2 and Cohort 3 will be selected based on PK/PD and safety data from the preceding cohort/s. The SDRT will review all available safety and tolerability data and PK/PD analysis outcomes from the previous cohort/s prior to inoculation of the next cohort. The study will conclude when sufficient data have been obtained to define the PK/PD parameters for pyronaridine (the primary endpoint).
 
A maximum sample size of 18 participants administered pyronaridine is expected to be sufficient to achieve the primary endpoint.
 
Participants will be confined in the clinical unit for at least 96 h (Days 8 - 12) to monitor the safety and tolerability of pyronaridine dosing and to ensure adequate clinical response against P. falciparum. During confinement, regular safety assessments will be performed and blood will be collected to monitor parasite clearance and pyronaridine concentration. If participants are clinically well at the end of the confinement period, they will be discharged and monitored on an outpatient basis up to Day 50±2.
 
Participants will receive compulsory antimalarial rescue treatment with Riamet® (artemether/lumefantrine) on Day 47±2 or earlier in the following cases:
 
 • Parasitaemia is not reduced by approximately 10-fold at the end of the 96 hour confinement period (Day 12) when compared with peak parasitaemia. • Parasite regrowth occurs after an initial reduction in parasitaemia, with regrowth defined as ≥ 5000 parasites/mL and a two-fold parasitaemia increase within 48 hours. • Volunteer discontinuation/withdrawal from the study. • Investigator's discretion in the interest of participant safety. 
Parasite lifecycle stages (including gametocytes) will be monitored at select time points during the study by collecting blood samples and using quantitative reverse-transcriptase polymerase chain reaction (qRT-PCR) targeting parasite lifecycle stage-specific mRNA transcripts.
 
If gametocytes are present as determined by qRT-PCR at any time point after the confinement period, a single dose of Primacin® will be administered at the Investigator's discretion. If an allergy or contraindication to Riamet® develops, Malarone®
		Dose group				1A (n=2)	1B (n=2)	1C (n=2)	Pyronaridine	360 mg	540 mg	720 mg

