6.3 MEASURES TO MINIMIZE BIAS: RANDOMISATION

All participants will receive an identification number (screening number) as soon as they have signed the informed consent form. Participants who meet the eligibility criteria and are enrolled in the study will be assigned an enrolment number on Day 0 immediately prior to administration of the malaria challenge agent. Participants will be randomised within each cohort to a dose group on Day 8, immediately prior to administration of the IMP. This is an open label study and therefore no blinding will be performed.

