7 STUDY INTERVENTIONS DISCONTINUATION AND PARTICIPANT DISCONTINUATION/WITHDRAWAL

7.1 DISCONTINUATION OF STUDY INTERVENTIONS

The Sponsor, SDRT, PI, approving HREC(s), and the TGA independently reserve the right to discontinue the trial at any time for safety or other reasons. This will be done in consultation with the Sponsor where practical. In the event of premature trial termination or suspension, the above-mentioned parties will be notified in writing by the terminator/suspender stating the reasons for early termination or suspension (with the exception of the TGA as it is the Sponsor's responsibility to notify regulatory authorities). After a decision to prematurely terminate the trial or to suspend the trial, the Sponsor and the PI will ensure that adequate consideration is given to protecting the participants' interest and safety. The PI must review all participants as soon as practicable and complete all required records.

7.1.1 CRITERIA FOR ADMINISTRATION OF RESCUE MEDICATION INSTEAD OF IMP DOSING ON DAY 8

Once inoculated, it is expected that some study participants will experience malaria symptoms and biological changes (i.e. mild ALT/AST elevation, mild decrease in neutrophil count). Therefore, the following criteria should be considered as guidance for the decision not to proceed with pyronaridine dosing on Day 8 and preference for rescue medication instead:

1. A participant experiences an SAE or \geq CTCAE Grade 3 event (e.g. inoculum-related events such as lymphopenia or neutropenia).
2. A participant has an ALT or AST $> 2 \times$ ULN or total bilirubin $> 1 \times$ ULN.
3. A participant with positive alcohol or urine drug screen.
4. A participant who tests positive for SARS-CoV-2 (section 8.3.7).
5. A participant with one of the following ECG abnormalities:
 - QTcF at any time >480 msec,
 - Bundle branch block (except right bundle branch block that was present prior to pyronaridine administration),
 - Any arrhythmia, except:
 - a. *Sinus bradycardia that is clinically asymptomatic, and not associated with any other relevant ECG abnormalities,*
 - b. *sinus tachycardia that is clinically asymptomatic, and not associated with any other relevant ECG abnormalities,*
 - c. *Respiratory sinus arrhythmia,*
 - d. *Wandering atrial pacemaker,*

- e. *Isolated, single premature atrial/ventricular complex (i.e., no bigeminy, trigeminy, couplets, triplets or salvos) that does not occur more than once in a particular ECG tracing.*

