7.2 VOLUNTEER DISCONTINUATION/WITHDRAWAL FROM THE STUDY

Participants are free to withdraw from participation in the trial at any time upon request.

An Investigator may discontinue or withdraw a participant from the trial for the following reasons:

- Pregnancy
- Significant trial intervention non-compliance
- If any clinical AE, laboratory abnormality, or other medical condition or situation occurs (or an exclusion criteria is revealed that was not previously recognised) such that continued participation in the trial would not be in the best interest of the participant

The reason for participant discontinuation or withdrawal from the trial will be recorded on the eCRF. Participants who sign the informed consent form and are randomised but do not receive malaria inoculation may be replaced. Participants who sign the informed consent form, and are randomised and receive malaria inoculation, and subsequently withdraw, or are withdrawn or discontinued from the trial, may be replaced after mutual agreement between the Sponsor and the PI. The decision regarding the replacement of participants will be documented.

Participants who have been inoculated and indicate they wish to withdraw from the trial must complete the full course of definitive antimalarial treatment.

Participants will be reminded of the importance of completing their antimalarial treatment. Additionally, the PI will demonstrate due diligence in following up with the participant to ensure antimalarial therapy has been completed successfully. Participants may also be treated with Primacin™ if gametocytaemia is suspected from parasite lifecycle qRT-PCR or by the presence of stable low-level parasitaemia to ensure complete clearance of gametocytes. The decision to administer Primacin™ will be made by the PI in consultation with the medical monitor.

If a participant is withdrawn from the trial, the Sponsor will be informed immediately. If there is a medical reason for withdrawal, the participant will remain under the supervision of the PI until satisfactory health has returned, or medical/clinical care has been transferred to the participant's general practitioner or to a hospital consultant.

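### The protocol gives two incompatible randomisation times, and under the earlier one an open-label dose allocation could be known before the partly discretionary Day 8 decision to dose

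*Protocol*

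**What the plan says.** Two times for randomisation stand in current text.

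- **Day of dosing.** The synopsis, Protocol 4.1 and 4.3, and SAP 3.1 describe each cohort as having up to three dose groups, "with participants randomised to a dose group on the day of dosing". Protocol 6.3 is more exact, and SAP 3.7 repeats it: "Participants will be randomised within each cohort to a dose group on Day 8, immediately prior to administration of the IMP".
- **Before Day 8.** Where a cohort tests more than one dose, the synopsis says "subjects will be randomised after inoculation day (Day 0) but prior to Day 8". Protocol 4.1 says the same without the bracket: "subjects will be randomised after inoculation day but prior to Day 8".

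Protocol 7.2 sets no time, but its replacement rule covers people who "are randomised but do not receive malaria inoculation may be replaced". That presupposes randomisation before Day 0. The following sentence in 7.2, carried into SAP 3.7, also lists randomisation ahead of inoculation.

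On blinding, Protocol 6.3 says: "This is an open label study and therefore no blinding will be performed". On the dosing decision, Protocol 7.1.1 says "the following criteria should be considered as guidance for the decision not to proceed with pyronaridine dosing on Day 8", and its last item lets the investigator withhold pyronaridine for safety signals outside the list.

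**The concern.** Protocol 6.3 is the section on measures to minimise bias. With no blinding and no allocation concealment described, what protection there is depends on when the allocation comes into being. If it exists before Day 8, whoever decides on dosing may know that a participant is due the highest or the lowest dose. Protocol 2.2.1 links pyronaridine to transaminase rises, so a borderline liver result in someone known to be allocated the top dose is a plausible case in which the allocation could sway the decision.

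A participant who is not dosed drops out of the IMP set (SAP 5.1.2) and the PD set (SAP 5.1.4). If withholding depended on allocated dose, the remaining dose groups would be selected. The outputs exposed are those that compare or tabulate by dose: dose-specific PRR48 with its omnibus test and pairwise contrasts (SAP 11.1.2), and the tables of treatment-emergent adverse events by dose group (SAP 11.3.1.2). In Cohort 1 each dose group has two participants, so one undosed participant is half a group.

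**Working it through.** **Step 1. The timing statements side by side.**

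| Place | Time of randomisation | Scope |
|---|---|---|
| Protocol synopsis, 4.1 (dosing paragraph), 4.3; SAP 3.1 | Day of dosing | Each cohort |
| Protocol 6.3; SAP 3.7 | Day 8, immediately before the IMP | Within each cohort |
| Protocol synopsis and 4.1 (paragraph on subsequent cohorts) | After Day 0, before Day 8 | Cohorts testing more than one dose |
| Protocol 7.2 and SAP 3.7 (replacement text) | None stated; wording presupposes before Day 0 | Withdrawn participants |

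Dosing is on Day 8, so the first two rows agree with each other and exclude the third. The third-row sentence follows one about subsequent cohorts and could be read as covering Cohorts 2 and 3 only. That does not remove the conflict, because the first two rows apply to every cohort.

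**Step 2. Order of events under the earlier time.** Protocol 8.1.5 places the ECG, the drug and alcohol screens, the SARS-CoV-2 rapid test and the review of the Day 7 bloods at Day 8 admission, before dosing. An allocation made before Day 8 therefore precedes the information on which the 7.1.1 decision rests. Randomisation after that decision is documented reverses the order.

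**Step 3. What later randomisation changes numerically.**

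Inputs: six participants in three groups of two (Protocol 4.1, Cohort 1), and a probability *p* that a participant is not dosed on Day 8. The documents do not give *p*; 0.05, 0.10 and 0.20 are assumed, with exclusions independent and unrelated to dose.

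Chance that anyone is excluded: 1 − (1 − p)^6 = 26%, 47%, 74%. This is the same under either timing, so it does not measure the benefit of the change.

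Chance that a whole dose group is emptied when allocation is made first:

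- Exactly two excluded: 3 of the 15 possible pairs are a complete group, so 3/15 = 0.20.
- Exactly three excluded: 3 groups × 4 choices of third person = 12 of the 20 possible triples contain a complete group, so 12/20 = 0.60.

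If the four or three people cleared are instead allocated in balance across three doses, no group is empty in either case. With four or more excluded, at most two people remain for three doses, so a group is empty under either timing.

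Avoidable chance = 0.20 × 15p²(1 − p)^4 + 0.60 × 20p³(1 − p)³

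| p | Two excluded | Three excluded | Avoidable | Any emptied group under early allocation, 1 − (1 − p²)³ |
|---|---|---|---|---|
| 0.05 | 0.0061 | 0.0013 | 0.7% | 0.7% |
| 0.10 | 0.0197 | 0.0087 | 2.8% | 3.0% |
| 0.20 | 0.0492 | 0.0492 | 9.8% | 11.5% |

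The last two columns differ by the cases with four or more exclusions.

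**The case against.** The best defence is that the documents largely settle the matter. The dedicated randomisation section and SAP 3.7 are explicit, and SAP 3.1 omits the pre-Day 8 sentence altogether. On this view one stray sentence, duplicated in the synopsis and 4.1, needs an editorial correction. That is fair as to the scale of the repair, but the sentence is operative text and staff running a multi-dose cohort cannot comply with both.

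Second, the bias route is not demonstrated. No passage says that an early allocation would be disclosed to the person deciding on dosing, and most 7.1.1 criteria are objective thresholds or test results. This stands: the documents support saying that allocation could be known, not that it will be. Yet the criteria are guidance, and discretion goes beyond the list.

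Third, depleted groups are partly handled. The review team sets doses between Day 0 and Day 8 according to the number inoculated (4.3) and reselects doses for later cohorts. Section 7.1.1 allows recruitment into later cohorts after more than two pre-dose discontinuations, and 7.2 allows replacement by agreement. These soften the loss of a group but do not address selection by known dose.

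Three stronger readings are tempting and unsupported. A reader might count three stated randomisation times, but 7.2 only implies one. A reader might take 26%, 47% or 74% as the harm of early allocation, but those are the chances of any exclusion, which the change leaves as they are. A reader might infer that the primary result is biased, but that analysis has no hypothesis test (9.1) and models each participant's measured concentrations and parasitaemia (9.4.2), so it does not rest on dose-group balance.

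**Conclusion.** The point holds as an inconsistency with a limited but real bias risk. Two incompatible randomisation times are in force, and following the earlier one would fix an open-label allocation ahead of a partly discretionary decision that determines who enters the IMP and PD sets. The risk falls on dose-specific PRR48, its between-dose test and the by-dose adverse event tables. The size of any selection bias cannot be calculated from the documents.

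The countable gain from later randomisation is modest: about 0.7%, 2.8% or 9.8% per cohort for an avoidably emptied dose group. It depends on the assumed exclusion rates, independent exclusions, balanced allocation of those cleared, and three groups of two. That layout is specified only for Cohort 1; later group sizes are left open. The case for the change rests on the conflict and the order of events, not on these percentages.

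**What to change.** In the synopsis and Protocol 4.1, replace the pre-Day 8 wording with randomisation on Day 8, after the decision to dose has been documented and immediately before the IMP. This agrees with 6.3 and SAP 3.7 and with the day-of-dosing text in the synopsis, 4.1, 4.3 and SAP 3.1. Correct the replacement wording in Protocol 7.2 and SAP 3.7 so that it no longer places randomisation before inoculation.

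If any cohort was allocated before Day 8, the study report should say so and list anyone randomised but not dosed by allocated group.

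The cost is a wording amendment. No dose, clinical dosing criterion or visit changes. The documents do not describe how allocations are generated or tablets dispensed, so the site should confirm that this can be done on the morning of Day 8, as 6.3 already requires.
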